### 16.1. Pregnancy Testing

WOCBP must have a negative serum pregnancy test ( $\beta$ HCG) at screening and a negative urine pregnancy test prior to dosing on each occasion.

Participants who are pregnant or breastfeeding are excluded from the study. Participants who return a positive urine pregnancy test at any study visit will be discontinued from study drug and a serum pregnancy test conducted. If the serum pregnancy test is also positive, the patient will be discontinued from the study and an early termination visit will be undertaken.

## 17. WITHDRAWAL

Participants will be informed that they are free to withdraw from the study.

The CPI may discontinue the study drug and/or withdraw a participant from the study if, in the Investigator's opinion, it is not in the best interest of the participant to continue the study, or the participant demonstrates a consistent pattern of non-compliance with study procedures. Site PIs should discuss with the CPI any participant cases where withdrawal should be considered.

---

Patients withdrawing from the study early should be strongly encouraged to perform the early termination visit as soon as possible following the last dose of study drug and the Follow-Up visit should be performed 7 days (+/- 2 days) after the last dose of study drug is taken. If the participant does not want to return to the clinic for the Early Termination or Follow-up visit, a phone call visit should be made to collect as much information as possible.

### 17.1. Replacement of participants

In Part A, a subject who is withdrawn from the Study before Day 4 (the second dose) for any reason other than a dose limiting toxicity will be replaced. A subject who has withdrawn after Day 4 is completed will not be replaced. This will ensure that two subjects take placebo at end dose level.

In Part B, a subject who is withdrawn from the Study before completion of Day 1 (the first dose) for any reason other than a dose limiting toxicity will be replaced. A subject who has withdrawn after Day 1 dosing is completed will, if possible, be replaced at the discretion of the sponsor and the Investigator.

Replaced subjects will take the same treatment as the original subject that is being replaced.

A termination case report form (CRF) page should be completed for every subject who received study medication whether or not the subject completed the study. The reason for any early discontinuation from the study will be indicated on this form.

### 17.2. General Considerations for Stopping Criteria

For Part A of the Study:

- If 1 or more participants exhibits an SAE, or a significant AE, that is determined to be related to the study drug, (ie Serious Adverse Reaction or a Suspected Unexpected Severe Adverse Reaction) the study will be halted. No further dosing, dose escalation or inclusion of any further participants at the same dose will occur without recommendation by the Data Safety Monitoring Committee (DSMC) as per the agreed DSMC charter.
- If 2 or more participants exhibit a moderate AE determined to be related to the study drug in the same system organ class (SOC, e.g., immune or gastrointestinal system, no further dosing, dose escalation or inclusion of any further participants at the same dose will occur without recommendation by the DSMC.
- If any participant exhibits a mild or moderate AE that in the Investigator's opinion may be an allergic reaction the study may be halted. No further dosing, dose escalation or inclusion of any further participants at the same dose will occur without recommendation by the DSMC.

For Part B of the Study:

- If 1 or more participants exhibits an SAE, or a significant AE, that is determined to be related to the study drug (i.e. a Serious Adverse Reaction or a Suspected Unexpected Severe Adverse Reaction) the study will be halted. No further dosing will occur without recommendation by the DSMC.
- If 2 or more participants exhibit a moderate AE determined to be related to the study drug in the same system organ class (SOC, e.g., immune or gastrointestinal system), the study will be halted. No further dosing, will occur without recommendation by the DSMC.

---

- If any participant exhibits a mild or moderate AE that in the Investigators opinion may be an allergic reaction the study may be halted. No further dosing, will occur without recommendation by the DSMC.

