### 20.3. Suspected unexpected serious adverse reactions

Suspected unexpected serious adverse reactions (SUSARs) are AEs that are believed to be related to an IMP and are both unexpected (i.e. the nature or intensity is not expected from the information provided in the Investigator's Brochure) and serious. SUSARs are subject to expedited reporting to the applicable regulatory authorities.

For regulatory reporting purposes, SUSARs will be unblinded.

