## 20.5. Severity (Intensity) of adverse event

Grade refers to the intensity of an AE and should not be confused with seriousness

**Grade 1** Mild; asymptomatic or mild symptoms; clinical or diagnostic observations only; intervention not indicated.

**Grade 2** Moderate; minimal, local or noninvasive intervention indicated; limiting age appropriate instrumental Activities of Daily Living (ADL\*).

**Grade 3** Severe or medically significant but not immediately life-threatening; hospitalisation or prolongation of hospitalisation indicated; disabling; limiting self-care ADLs.

**Grade 4** Life-threatening consequences; urgent intervention indicated.

**Grade 5** Death related to AE.

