## 20.6. Serious adverse event

A serious adverse event (SAE) is any untoward medical occurrence or effect that, at any dose:

- Results in death,
- Is life-threatening.

Life-threatening in the definition of serious refers to an event in which the participant was at risk of death at the time of the event, it does not refer to an event which hypothetically might have caused death if it were more severe.

- Requires inpatient hospitalisation or prolongation of existing hospitalisation.

Hospitalisation is defined as inpatient admission or care regardless of duration. Out-patient treatment in an emergency room is not in itself an SAE, although the reasons for it may be.

Elective surgery, or hospital admissions and/or surgical operations planned before or during this study are not considered Aes if the illness or disease existed before the participant was enrolled in the study, provided that it did not deteriorate in an unexpected way during the study.

- Results in persistent or significant disability/incapacity.
- Is a congenital anomaly/birth defect.
- Is medically important or is a medically significant event.

Medical and scientific judgement is required to decide if prompt notification is required in situations that the investigator regards as medically important that did not strictly meet the criteria above but may have jeopardised the participant or required intervention to prevent one of the outcomes listed above, or that would suggest any significant hazard, contraindication, side effect or precaution that may be associated with the use of the IMP. Such events should also be considered as serious.

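### Stopping criteria 2 and 3 omit "or worse", so as printed two related moderate AEs in one organ class halt dosing but two expected, severe, non-serious ones do not

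*Protocol*

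**What the plan says.** Protocol 17.2 gives three criteria, in parallel for Part A and Part B.

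- **Criterion 1** halts the study after one participant has a related SAE or *significant AE*. An 'i.e.' in brackets explains this as a "Serious Adverse Reaction or a Suspected Unexpected Severe Adverse Reaction".
- **Criterion 2** stops dosing pending a DSMC recommendation: "If 2 or more participants exhibit a moderate AE determined to be related to the study drug in the same system organ class".
- **Criterion 3** concerns possible allergy: "If any participant exhibits a mild or moderate AE that in the Investigator's opinion may be an allergic reaction the study may be halted".

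Section 20.5 lists mild, moderate and severe as Grades 1, 2 and 3, and warns: "Grade refers to the intensity of an AE and should not be confused with seriousness". Grade 3 begins "Severe or medically significant but not immediately life-threatening". Section 20.3 defines a SUSAR by relatedness, seriousness and unexpectedness, where unexpected means that "the nature or intensity is not expected from the information provided" in the Investigator's Brochure. The list of serious outcomes in 20.6 includes an event that "Is medically important or is a medically significant event".

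**The concern.** A stopping rule should be monotone: if a set of events stops dosing, a worse set should stop it too. Criteria 2 and 3 name a grade without making it a minimum. Criterion 1 does not take in everything above that grade, because its bracketed explanation admits only reactions that are serious, or unexpected and severe. Related AEs that are severe, expected and non-serious fall between the two.

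What is at stake is participant protection during IV dosing. The highest earlier IV dose described in 5.2 is 400 µg/kg (METAOD001). Part A runs from 0.8 to 1.8 mg/kg, which is 0.8/0.4 = 2 to 1.8/0.4 = 4.5 times that dose. Criteria 1 and 2 are the mandatory triggers. DSMC monitoring (21.7), withdrawal by the investigator (17) and suspension by the sponsor (19.1) are discretionary.

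**Working it through.** The plan gives no operating characteristics for these rules, so there is no figure to reproduce. The check is logical.

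**Inputs.** Criteria 1 to 3 come from 17.2, the grades from 20.5 and expectedness from 20.3. Take two participants, each with one related, non-serious, non-allergic AE in the same organ class. Each AE is one of three kinds: moderate (M), severe and expected (Se), or severe and unexpected (Su). That gives 6 unordered pairs.

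**Three readings of criterion 1.**
- *As printed*: it fires if either AE is Su.
- *'Severe' is a slip for 'Serious'*, the term used in 20.3: it fires for neither, since no AE here is serious.
- *'Significant AE' means Grade 3*, following the Grade 3 wording in 20.5: it fires if either AE is severe.

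As printed, criterion 2 fires only for M+M.

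| Pair | As printed | Severe = Serious | Significant = Grade 3 | Criterion 2 at Grade 2 or higher |
|---|---|---|---|---|
| M+M | stop | stop | stop | stop |
| M+Se | **no stop** | no stop | stop | stop |
| M+Su | stop | no stop | stop | stop |
| Se+Se | **no stop** | no stop | stop | stop |
| Se+Su | stop | no stop | stop | stop |
| Su+Su | stop | no stop | stop | stop |
| Total | 4 of 6 | 1 of 6 | 6 of 6 | 6 of 6 |

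The last column follows by construction: every pair has two participants at Grade 2 or above, so the amended criterion fires whichever reading of criterion 1 is taken. The counts are kinds of case, not likelihoods. As printed, even six Se events would meet no criterion.

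**Criterion 3.** A mild possible allergic reaction is named. A severe, non-serious one is not. Criterion 1 would take it only if it were both unexpected and judged related, and criterion 3 itself does not require relatedness.

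**Illustration with assumed rates.** The documents give no rates. Suppose 20% of actively dosed participants have a related AE of Grade 2 or 3 in one organ class, at most one each and independently, with all severe ones expected and non-serious. With moderate-AE probability p, criterion 2 as printed fires with probability P = 1 − (1 − p)^n − n·p·(1 − p)^(n−1). With 'Grade 2 or higher', p becomes 0.20. For n = 6 and p = 0.10: 1 − 0.531 − 0.354 = 0.114 (from unrounded terms). At p = 0.20: 1 − 0.262 − 0.393 = 0.345.

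| Moderate / severe | n = 6 (one Part A dose), printed | n = 6, amended | n = 20 (Part B maximum), printed | n = 20, amended |
|---|---|---|---|---|
| 20% / 0% | 0.345 | 0.345 | 0.931 | 0.931 |
| 15% / 5% | 0.224 | 0.345 | 0.824 | 0.931 |
| 10% / 10% | 0.114 | 0.345 | 0.608 | 0.931 |
| 5% / 15% | 0.033 | 0.345 | 0.264 | 0.931 |
| 0% / 20% | 0 | 0.345 | 0 | 0.931 |

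As the same events become more severe, the printed criterion becomes less likely to fire. The table shows direction only and is not a forecast.

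**Does the category occur?** In 5.2, severe AEs called related or possibly related, with no related SAE in the same study, appear in 1 of 23 participants in METAOD002 (IV, chest pain) and 3 of 300 in METAOD005 (oral, three different symptoms, arm not stated). METAOD006 had 2 related SAEs among 502 participants, both syncope, one of them after placebo. So a severe related AE can be non-serious. These data do not show two in one organ class, or that any would count as expected.

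**The case against.** The strongest objection is that the gap may be empty. It needs AEs that are severe, related, non-serious and expected, and expectedness turns on intensity as well as nature. If the Investigator's Brochure lists no reaction as expected at severe intensity, every related severe AE is unexpected and criterion 1 halts the study after one. Section 5.2 reports no pattern of severe, related AEs. Grade 3 also overlaps the definition of serious: hospitalisation, disability and medical significance appear in both 20.5 and 20.6. This stands as a limit on how often the gap would matter. It does not repair the text, and the Brochure was not available.

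The second objection is that the criteria form a ladder in which criterion 1 is meant to cover all higher grades, with *significant AE* meaning Grade 3. That may be the intent, and it would close the gap in criterion 2. But it sets aside the printed 'i.e.'. Section 17.2 also writes 'or more' for its participant counts and not for grade, and SAP 12.1 writes 'Grade 3+' when a grade and above is meant.

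Third, there are other safeguards: the Part A limit of one dose-limiting toxicity in six (7.3), review of safety bloods before the second and third Part A doses (9.6.9), presentation of Part A safety data to the ethics committee (19.2), and DSMC monitoring. None forces a halt in this case. Section 7.3 sets the maximum tolerated dose, using a toxicity term that the protocol does not define. The DSMC charter was not available and may settle the point.

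**Conclusion.** The concern holds. Read exactly, 17.2 stops dosing for two related moderate AEs in one organ class but not for M+Se or Se+Se, both of which are worse. Criterion 3 has the same omission. Depending on how criterion 1 is read, 4, 1 or 6 of the 6 pairings stop dosing, which is too wide a spread for a mandatory rule.

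The conclusion rests on taking the bracketed 'i.e.' as exhaustive and on at least some severe reactions being expected and non-serious. If *significant AE* means any Grade 3 event, the criterion 2 gap disappears. Its practical reach is probably narrow and cannot be quantified from these documents. It affects participant safety oversight and no efficacy endpoint. It should be corrected; confidence is medium because the Brochure and the charter were not seen.

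**What to change.** In both Parts:

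1. Change criterion 2 to moderate or worse (Grade 2 or higher).
2. Change criterion 3 to an AE of any grade that may be an allergic reaction.
3. Match the DSMC charter to the new wording.
4. Leave to the sponsor and DSMC whether a single related Grade 3 AE should halt the study under criterion 1. The change to criterion 2 alone does not make it do so.
5. Do not replace 'Severe' with 'Serious' in criterion 1 unless a trigger for unexpected severe reactions is kept. Without one, and without the change to criterion 2, the count falls to 1 of 6.

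The cost is a protocol amendment with ethics committee review (22.4), an edit to the charter, and possibly an extra DSMC review with a short pause in dosing. No procedures are added.

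SAP 2.5 records a recommendation to close the study on 12 May 2023. If dosing has ended, check whether any related Grade 3 AE failed to trigger a criterion. The Grade 3+ and related TEAE summaries planned in SAP 12.1 are the place to start. Carry the corrected wording into later IV protocols.

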## 18. PROHIBITIONS AND RESTRICTIONS IN THE STUDY

### 18.1. Prohibited medications

Participants must abstain from alcohol for 24 hours prior to each dosing occasion. Illicit drugs are prohibited. Participants should also avoid caffeine for 48 hours and grapefruit juice for 24 hours prior to arrival to study visit.

Use of prescription or over the counter medications and vaccines are prohibited within 14 days of investigational product administration and during the study, with the exception of current medications provided the dose has been stable for at least 14 days, contraceptive medications, paracetamol, oral non-steroidal anti-inflammatory agents and vitamins;

Participants should also not receive any other investigational products during the study.

Participants should also not initiate any new exercise or physical therapy regimens during the study. Exercise and physical therapy regimens that were in place at the Screening visit may be continued in a stable manner during the study.

### 18.2. Contraception

A female participant is eligible to participate if she is not pregnant, not breastfeeding, and at least 1 of the following conditions applies:

- Not of childbearing potential, defined as surgically sterile (documented hysterectomy, bilateral salpingectomy or bilateral oophorectomy) or postmenopausal (no menses for 12 months without an alternative medical cause. A high follicle stimulating hormone (FSH) level in the postmenopausal range may be used to confirm a postmenopausal state in women not using hormonal contraception or hormonal replacement therapy; however, in the absence of 12 months of amenorrhea, a single FSH measurement is insufficient);
- Of childbearing potential and agrees to use a highly effective method of contraception consistently during the treatment period and for at least 60 days following completion of study.
- A male participant with a female partner of childbearing potential is eligible to participate if he agrees to use acceptable contraception during the treatment period and for at least 60 days after the last dose of study treatment and refrains from donating sperm during this period;

To prevent pregnancy in a female subject of child bearing potential (FOCBP), the FOCBP must use a highly effective method of contraception (failure rate of <1%), during the study and for 60 days after the last dose of IMP. Such methods include:

- Abstinence from heterosexual intercourse. This should be the subject's usual and preferred lifestyle OR
- Consistent and correct use of a highly-effective form of contraception, such as:
  - combined (estrogen and progestogen containing) hormonal contraception associated with inhibition of ovulation (oral, intravaginal or transdermal administration),

- progestogen-only hormonal contraception associated with inhibition of ovulation (oral, injectable or implantable administration)
- intrauterine device
- intrauterine hormone-releasing system
- bilateral tubal occlusion OR
- Vasectomised partner, provided that the partner is the sole sexual partner and that the vasectomised partner has received medical assessment of the surgical success of the vasectomy

Periodic abstinence (e.g. calendar, ovulation, symptothermal, post-ovulation methods) and withdrawal are not acceptable methods of contraception.

## 19. Study Oversight

### 19.1. Suspension or premature termination of the study

Conditions may arise during the study that could prompt the study to be halted or the study site to be terminated. The sponsor may terminate part of, or the entire study for safety, administrative, or commercial reasons. Conditions that may prompt such considerations include, but are not limited to, the following:

- The discovery of unexpected, serious, or unacceptable risk to participants enrolled in the study;
- A decision on the part of Sponsor to suspend, discontinue, or shorten the study;
- Study conduct at a study site may warrant termination under conditions that include the following:
  - Failure of investigator(s) to enrol eligible participants into the study;
  - Failure of the investigator to comply with country-specific regulations;
  - Submission of false information from the research facility to the sponsor, the clinical monitor, or a regulatory authority;
  - Insufficient adherence to protocol requirements;
  - A conflict of interest of the investigator, his/her institution, or site personnel that could negatively impact the integrity of the clinical study;
  - Institution or Ethics Committee under investigation for cause by a regulatory authority.

Any decision by the sponsor on stopping or restarting the study must be discussed with the investigator. All actions are to be documented and the Ethics Committee (EC) and regulatory (competent) authority notified in writing as required by local regulations. Should a protocol amendment be required, this will be managed in accordance with Section 22.4. The study must not recommence recruitment or dosing until approval is received in writing from the EC (if/as required by the EC). If the study is to be terminated for safety reasons, any further administration of IMP will be stopped.

If the study is terminated for safety reasons, participants will be followed up for a minimum of one week following the last exposure to IMP, at which time an End of Study visit should be conducted. Refer to Schedule 1 and 2 for follow up assessments. Any AEs/SAEs ongoing at the time of the End of Study visit will be followed to resolution or stabilisation (whichever is the sooner).

## 19.2. Continuation on to Part B

At the conclusion of Part A of the study safety data and PK data will be collated and presented to HREC along with the justification for dose level and dose interval for Part B.

## 20. ADVERSE EVENTS

### 20.1. Adverse event

An adverse event is any untoward medical occurrence in a patient or clinical investigation participant administered a pharmaceutical product and may not necessarily have a causal relationship with the administered treatment.

An AE can therefore be any unfavourable and unintended sign (including an abnormal laboratory finding), symptom, or disease temporally associated with the use of a medicinal (investigational) product, whether or not it is related to the medicinal (investigational) product. This includes an exacerbation of pre-existing conditions or events, intercurrent illnesses, drug interaction or any worsening (i.e. any clinically significant adverse change in frequency and/or intensity) of a pre-existing condition, which is temporally associated with the use of the sponsor's product. Anticipated fluctuations of pre-existing conditions, including the disease under study, that do not represent a clinically significant exacerbation or worsening need not be considered AEs.

Laboratory reference ranges are defined by upper or lower limits of parameters of the respective laboratory. The investigator should ensure that each parameter out of the normal range is assessed for clinical significance and the potential for being an AE (refer to Schedule 1 and 2). An adverse event is defined as 'serious' when it meets one of the pre-defined outcomes as described in Section 12.1.6.

### 20.2. Adverse drug reaction/Suspected adverse (drug) reaction

An adverse drug reaction (ADR) is any AE for which there is a reasonable possibility that the drug caused the AE. Reasonable possibility means there is evidence to suggest a causal relationship between the IMP and the adverse event.

### 20.3. Suspected unexpected serious adverse reactions

Suspected unexpected serious adverse reactions (SUSARs) are AEs that are believed to be related to an IMP and are both unexpected (i.e. the nature or intensity is not expected from the information provided in the Investigator's Brochure) and serious. SUSARs are subject to expedited reporting to the applicable regulatory authorities.

For regulatory reporting purposes, SUSARs will be unblinded.

